4.16 Lost to Follow-Up

A study subject will be considered lost to follow-up if he or she repeatedly fails to return for scheduled visits and is unable to be contacted by the study site.

The following actions must be taken if a participant fails to return to the clinic for a required study visit:

- The site must attempt to contact the participant and reschedule the missed visit as soon as possible, counsel the participant on the importance of maintaining the assigned visit schedule and ascertain whether or not the participant wishes to and/or will continue in the study.
- For the surgical excision visit (Visit 6), the sites must confirm the surgical excision date with the participant 1-2 times, 1 week to 1 day prior to the visit day and reiterate the importance of completing the surgical excision visit in order to ensure the cancer does not return or spread. If the subject does not confirm and/or does not come in on their scheduled excision date, the site must attempt to contact the participant with at least three phone calls. If the site cannot reach the participant, the site is to send a certified letter to the participant's last known mailing address or local equivalent methods.
- Before a participant is deemed lost to follow up, the investigator or designee must make every effort to regain contact with the participant (where possible, 3 telephone calls and, if necessary, a certified letter to the participant's last known mailing address or local equivalent methods). These contact attempts are to be documented in the participant's medical record.
- If the participant continues to be unreachable, he/she will be considered to have withdrawn from the study.

5.0 BENEFITS AND RISKS

5.1 Benefits

There are no guaranteed benefits from participation in this study. Participation in the study offers another dermatological approach to accomplish the same clinical effect as the typical topicals, surgical devices or surgical excision currently used to treat patients with BCC lesions. The information learned from this study may contribute to the ultimate use of a safer and more effective device and the availability of the device to treat benign and non-benign lesions as an alternative for use in future patients.

5.2 Risks

For detailed information on the risks of the devices used in the study procedure, including a complete list of warnings, precautions, and potential adverse events, please refer to the Instructions for Use (IFU) for the Pulse Bioscience CellFX® System.

An additional risk for study participants is the delay in performing surgical excision of the tumor; however, basal cell carcinomas are slow-growing, so a delay of 60 days is considered a minimal risk. The wait times for standard surgical excisions are often longer than 60 days in some areas and practices. Because biopsy and surgical excision are standard of care for basal cell carcinoma and will also be occurring in this study, risks of these procedures are not considered in the benefit/risk assessment.

5.3 Mitigation of Risks

As with any dermatological procedure, appropriate safety precautions will be followed. Risks observed or theoretical adverse events have been mitigated through the Instructions for Use, physician training, and patient selection in the study protocol. The subject will receive full care of their BCC lesion(s).

All efforts will be made to minimize these risks by:

- Site Selection
- Patient Population that represents the demographics of the U.S
- Ensuring compliance to the protocol and IFU
- Study monitoring
- Safety processes-protocol adverse events reporting requirements

The following plan is set in place in order to mitigate the risk of the study participant treated with the CellFX system not returning for their surgical excision visit to receive full care of their BCC lesion(s):

- Prominent language is added to the Informed Consent Form to emphasize that the CellFX treatment has not yet been shown to remove all cells from a skin tumor, and therefore surgical removal is of the utmost importance to ensure that the cancer does not return or spread.
- Training of the PI and their clinical study staff will emphasize the importance of subject selection in selecting subjects who will commit to all study visits, an explanation of the importance for all subjects to complete their surgical excision of the diagnosed BCC lesion, training to remind and confirm the study visits with the subjects at each visit, with emphasis on the surgical excision visit.
- Subject compensation is structured to motivate the subject to complete the surgical excision, and safety follow up visits with the highest compensation assigned to the surgical excision visit (Visit 6), higher monetary values assigned to the later follow-up visits (visits 7-9), as well as an all-visit bonus offered for subjects who complete all study visits.

- Site compensation includes an all-visit bonus to motivate the site to closely follow-up with the study subjects to ensure all visits are completed.
- Remote and on-site monitoring of subject visits at all participating sites to ensure compliance of subject attending scheduled study visits.

6.0 STATISTICAL CONSIDERATIONS

6.1 General Approach

For descriptive statistics, counts and percentages will be calculated for categorical variables. Continuous variables will be summarized using the mean, standard deviation, median, minimum and maximum. No inferential tests are planned for this study, but 2-sided confidence intervals will be produced where appropriate. Where 2-sided p-values are calculated, they should be interpreted as descriptive only.

6.2 Analysis of the Primary Effectiveness Endpoint

The count and proportion with the primary endpoint of histological clearance will be calculated along with a 95% confidence interval (CI). The primary population for this analysis will be the Per-Protocol population, though estimates will be produced for the modified intent-to-treat/ safety population (patients who begin treatment) and Complete Treatment population (subjects who complete all required cycles of treatment).

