3.0 PROTOCOL

3.1 Study Objectives

The primary objectives of this study are to evaluate the safety and effectiveness of the CellFX System in adults with low-risk basal cell carcinoma. Table 1 below reflects the study endpoints associated with the two objectives.

Table 1. Study Objectives and Endpoints

Objectives	Endpoints
Safety To evaluate the safety of the CellFX System in adults with low-risk basal cell carcinoma	Primary: 
 • No serious adverse events related to CellFX Treatment or Procedure Secondary: 
 • Local Skin Reactions (Investigator) • Procedural pain assessment (Subject)
Effectiveness To evaluate the effectiveness of the CellFX System in adults with low-risk basal cell carcinoma	Primary: 
 • Complete histological clearance of the target lesion on microscopic evaluation of hematoxylin and eosin stains Secondary: 
 • Visible/clinical clearance of the target lesion by clinical/dermatoscopic evaluation • Partial response of the study lesion as assessed by WHO criteria ($\geq 50\%$ decrease in the product of the longest perpendicular diameters of each target lesion) • SCAR-Q Appearance Scale (Subject) • Manchester Scar Scale (Investigator) • Healing assessment questions (Investigator)

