4.15 Discontinuation of CellFX Treatment Session

A participant may be discontinued from treatment with the CellFX System prior to completion of the entire treatment session in the event of intolerable pain or system failure of the CellFX System. If the study subject elects not to complete the treatment session, a study exit form shall be completed and documented as early termination. System failure of the CellFX System or component failure shall be documented on the Device Malfunction Form.

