6.3 Analysis of Secondary Endpoints

No formal hypothesis testing is planned for secondary endpoints. Any p-values comparing groups should be considered descriptive. The secondary endpoints will be evaluated using the modified intent-to-treat/ safety population, but these analyses may be repeated for complete treatment and per-protocol populations as well.

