6.6 Populations for Analyses

The following populations are defined in Table 5.

Table 5. Population Descriptions for Analysis

Population	Description
Modified Intent-to-treat / Safety Population	All enrolled participants who began treatment with the CellFX system, irrespective of completed study treatment session, subsequent withdrawal, or deviation from the protocol.
Complete Treatment	This population consists of mITT participants who completed the entire CellFX treatment session.
Per-Protocol	Participants who received treatment, completed the CellFX treatment session, excision surgery and all required study visits.

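### The primary histological clearance rate is taken in the Per-Protocol population, which excludes stopped sessions and, read literally, some valid Day-60 results; it may overstate clearance, and the planned mITT estimate should be primary

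*Combined protocol and SAP*

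**What the plan says.** Section 3.1 (Table 1) defines the primary effectiveness endpoint as "Complete histological clearance of the target lesion on microscopic evaluation of hematoxylin and eosin stains". The tissue comes from the excision at Visit 6, 60 days after treatment.

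Section 6.2 names the main analysis set for this endpoint: "The primary population for this analysis will be the Per-Protocol population". The same sentence continues: "though estimates will be produced for the modified intent-to-treat/ safety population (patients who begin treatment) and Complete Treatment population". Three estimates of histological clearance are therefore planned, and the Per-Protocol one is designated primary.

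Table 5 in section 6.6 defines the sets. Per-Protocol is "Participants who received treatment, completed the CellFX treatment session, excision surgery and all required study visits". The mITT/safety set is "All enrolled participants who began treatment with the CellFX system, irrespective of completed study treatment session, subsequent withdrawal, or deviation from the protocol".

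Section 4.15 gives the grounds for cutting a session short. A participant may be taken off treatment "prior to completion of the entire treatment session in the event of intolerable pain or system failure of the CellFX System". A subject who chooses not to finish is recorded as an early termination on a study exit form.

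Section 6.3 takes a different default: "The secondary endpoints will be evaluated using the modified intent-to-treat/ safety population". This covers clinical clearance (6.3.2) and WHO partial response (6.3.3), with optional repeats in the other two sets.

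**The concern.** Membership of Per-Protocol is decided by what happens after treatment starts. Intolerable pain and system failure are both shortcomings of the treatment under evaluation, yet a subject stopped for either leaves both numerator and denominator of the headline rate. There is no control arm in which a similar selection might offset this.

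The requirement for all visits adds a second exclusion. The endpoint is fixed at excision, but visits continue for 60 days afterwards (Visits 7 to 9). Taken at its word, Table 5 drops a subject with a readable Day-60 specimen for missing one of those visits. That has no bearing on whether the lesion was cleared.

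Section 3.1 asks about effectiveness in adults with low-risk basal cell carcinoma, which is a wider group than those who completed everything. Section 1.6 says the data will help to choose a treatment and design a pivotal study, so a rate from a selected group could be carried into that design.

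**Working it through.** The plan states no expected clearance rate, stopping rate, dropout rate or sample-size formula, so it has no figure to reproduce. The check asks how far the choice of population can move the rate.

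**Inputs from the documents.** At most 30 subjects are treated (6.5). Withdrawn subjects are not replaced (4.14). A 95% confidence interval is planned with no method named (6.2).

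**Assumptions.** All 30 are treated, with one lesion per subject. The number k outside Per-Protocol and the number x cleared within it are chosen for illustration. Intervals are exact (Clopper-Pearson).

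**Formulas.** With N = 30:
- Per-Protocol rate = x/(N − k).
- mITT rate, if those outside Per-Protocol count as not cleared = x/N.
- mITT rate, if those outside Per-Protocol in fact cleared = (x + k)/N.
- Gap in the first mITT case = x/(N − k) − x/N = xk/[N(N − k)].
- For x out of n, the exact lower limit is the 2.5% quantile of Beta(x, n − x + 1), and the upper limit is the 97.5% quantile of Beta(x + 1, n − x). When x = n the upper limit is 100%.

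**Separating the two sources.** Suppose 26 subjects are in Per-Protocol and all clear, two sessions are stopped without clearance, and two further subjects have no histology.
- Per-Protocol: 26/26 = 100% (86.8-100%).
- Adding the two stopped sessions: 26/28 = 92.9% (76.5-99.1%), a fall of 7.1 points.
- Adding the two without histology as not cleared: 26/30 = 86.7% (69.3-96.2%), a further 6.2 points.

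The total fall is 13.3 points. About half comes from the stopped sessions. The rest comes from the rule chosen for missing histology. If the two subjects without histology had cleared, the rate would be 28/30 = 93.3% (77.9-99.2%).

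**Range over k.** The first three rows take everyone in Per-Protocol as cleared; the fourth allows two Per-Protocol failures.

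| k | Per-Protocol | mITT, others not cleared | Gap (points) |
|---|---|---|---|
| 1 | 29/29 = 100% (88.1-100%) | 29/30 = 96.7% (82.8-99.9%) | 3.3 |
| 3 | 27/27 = 100% (87.2-100%) | 27/30 = 90.0% (73.5-97.9%) | 10.0 |
| 6 | 24/24 = 100% (85.8-100%) | 24/30 = 80.0% (61.4-92.3%) | 20.0 |
| 3 | 25/27 = 92.6% (75.7-99.1%) | 25/30 = 83.3% (65.3-94.4%) | 9.3 |

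Check of the gap formula at k = 3, x = 27: 27 × 3/(30 × 27) = 0.10.

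**The other direction.** With k = 0 the gap is zero. If the three subjects in the last row had in fact cleared, for example because they only missed a late visit, mITT is 28/30 = 93.3% against 92.6% for Per-Protocol. Per-Protocol is then lower by 0.7 points.

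**The case against.** **The mITT figure is already promised.** This stands. A reader might infer from sections 6.2 and 6.3 that histological and clinical clearance cannot be compared because they rest on different subjects. The documents do not support that: section 6.2 commits to an mITT histology estimate, and section 6.3 evaluates clinical clearance in mITT. Only the two designated results differ in population, and that is an open choice.

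**Missing data are addressed.** Section 6.9 plans a comparison with a longitudinal model and a tipping-point analysis at 60 days. This stands in part. Per-Protocol requires excision, so it removes most missing histology by definition and leaves the tipping-point analysis little to act on for the headline figure.

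**Relabelling the population may not bring stopped subjects back.** A subject who elects to stop exits under section 4.15 and may have no Day-60 data. The mITT clinical rates could then lack the same people. This stands, and it is why the fix needs a rule for missing histology, which the plan does not give.

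**Stopped sessions may be rare.** An analgesic is given before treatment (4.5.3), and section 1.5 reports no device or procedure complications in about 700 subjects. That bears on the likely size of k, although the documents give no count of stopped sessions.

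**This is a descriptive feasibility study.** Section 6.1 plans no inferential tests, and there is no success threshold, so no error rate is affected. Clearance among lesions fully treated and excised is a fair question at this stage. Both points stand. They support keeping Per-Protocol as a supportive estimate and limit the seriousness of the point.

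**Conclusion.** The point holds as a cheap improvement. Followed as written, the plan gives a headline rate that omits subjects whose session failed for pain or equipment reasons and, on a literal reading of Table 5, subjects with usable Day-60 histology who missed a later visit. The mITT estimate, which lies closer to the question in section 3.1, is planned but ranked below it.

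A reader might go further and conclude that effectiveness is overstated. The documents do not show that, because they give neither the number outside Per-Protocol nor the outcomes of those subjects. On assumed counts with 30 treated and those outside counted as not cleared, the gap is about 3 points for one exclusion, 9 to 10 for three and 18 to 20 for six. It is zero with no exclusions and can reverse slightly if the excluded subjects cleared. The supportable statement is that the Per-Protocol headline may overstate clearance.

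**What to change.** In section 6.2:
- Make mITT/safety the primary population for histological clearance, matching section 6.3, and keep Complete Treatment and Per-Protocol as supportive.
- Use every available Day-60 histology result, whatever the attendance at later visits.
- Count a session stopped for pain or system failure as not cleared unless histology shows clearance.
- Count subjects who lack histology for other reasons as not cleared in the primary estimate. Show beside it the estimate from observed histology and the tipping-point range from section 6.9.

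**Cost.** No new data are needed, and all three estimates are already planned. The rule for missing histology is nevertheless a real addition to the plan, so it should be fixed before results are seen. The headline rate may be less favourable. Counting losses unrelated to treatment as not cleared is conservative and can understate clearance, which is the reason for showing the observed-histology estimate and the range alongside.

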6.3 Analysis of Secondary Endpoints

No formal hypothesis testing is planned for secondary endpoints. Any p-values comparing groups should be considered descriptive. The secondary endpoints will be evaluated using the modified intent-to-treat/ safety population, but these analyses may be repeated for complete treatment and per-protocol populations as well.

6.3.1 Change in Lesion Size

Lesion size (as measured by the product of the longest perpendicular diameters) will be calculated at baseline and at follow-up day 60 post-NPS treatment. The two longest diameters (longest length and longest perpendicular width) of each study lesion will be measured and the product will be calculated for each individual study lesion at baseline and at 60 days-post NPS treatment study visits. Calipers will be provided to each study site to perform the measurements per standardized procedures. A standard adhesive ruler will also be included in photographs taken of each study lesion. Within-lesion change in lesion size from baseline to the 60-Day follow-up time-point will be calculated. A mixed model for repeated measures will be used to estimate the mean reduction and its 95% confidence interval. Baseline lesion size will be included as a fixed effect.

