3.2 Study Design

This study is designed as a prospective, multicenter IDE feasibility study in up to 30 adult participants with low-risk basal cell carcinoma utilizing the CellFX System at up to 6 sites within the United States. The study will consist of a single treatment session with the CellFX System followed by surgical tumor excision (with 5 mm margins) 60 days post-treatment.

Eligible subjects with 1-2 histologically confirmed, primary BCC lesion(s) who meet the inclusion and exclusion criteria will be enrolled. The BCC lesion(s) may be present anywhere on the body except neck, axilla, hands, feet, or genitals. In cases where the subject has more than 1-2 BCC lesions that meet the study criteria, the PI will select the lesion(s) to include in the study.

The subject will receive treatment of their confirmed BCC lesion(s) with the CellFX system. The treatment area will be evaluated at 3-days, 7-days, 14-days, 30-days and 60-days post-NPS treatment. At the 60-day follow-up visit, participants will undergo complete surgical excision of the tumor plus 5 mm margins. The subject will return for 3 more follow-up visits post-excision at 14 days (suture removal), 30 days and 60 days (typical skin check post-surgical excision) for a total of 9 study visits. The 3-day, 7-day, and 30-day post-NPS treatment follow-up visits as well as the 30-day post-surgical excision visit may be performed as telemedicine visits.

The excised tissue at the 60-day post-treatment visit will be shipped for histological analysis. Preparation and analysis of the excised tissue will be performed by Pinkus Dermatopathology Laboratory and a board certified dermatopathologist who has extensive experience in interpreting cutaneous neoplasms. Details of the preparation, shipment and analysis of the excised tissue are provided in the Tissue Handling and Analysis Procedure.

Photography of the study lesion(s) will be captured along with the investigator's assessments at all in-office visits. Detailed instructions for photography of the lesion area are provided in the photography instruction manual.

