3.5 Number of Subjects

Up to 30 subjects at up to 6 sites will be enrolled.

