4.2.1 Inclusion Criteria

Candidates for this study must meet **ALL** the following criteria:

1. Subject is at least 22 and no older than 85 years of age.
2. Subject has 1-2 primary, non-recurrent, superficial, or nodular visible basal cell carcinoma lesion up to 1.5 cm in size with well-defined borders that has been verified by biopsy.
3. Lesion(s) is appropriate for full linear excision with 5 mm margins.
4. Subject is capable of giving signed informed consent, which includes compliance with the requirements and restrictions listed in the ICF and in this protocol.

5. Subject gives voluntary, written informed consent to participate in this clinical investigation and from whom consent has been obtained.
6. Subject is willing to have BCC lesion(s) treated in a single treatment session and must comply with all study procedures including follow-up visits.
7. Subject consents to have photographs taken of the BCC lesion(s).
8. Subject agrees to refrain from using all other lesion removal products or treatments (topical medication including over-the-counter medications or treatments from PI or another physician) during the study period.
9. Subject agrees to refrain from prolonged sun exposure of the treatment area during the study period.

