6.3.2 Lesion Reduction Category

The visible/clinical clearance of the target lesions will be rated according to the lesion reduction categories listed in Table 4. The lesion reduction category will be derived from the lesion size measurements at baseline and follow-up day 60 Post-NPS treatment described in **Section 6.3.1**. The % reduction will be calculated as the change in lesion size divided by the baseline value. This percentage will be categorized according to the table 4 below:

Table 4. BCC Lesion Reduction Categories

BCC Lesion Reduction Categories			
CLEAR 0mm/100% reduction	MOSTLY CLEAR 99-51% reduction	PARTIALLY CLEAR 50-25% reduction	NOT CLEAR <25% reduction

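### The 95% CI for mean lesion-size reduction adjusts for baseline size in a single-arm study, so as an interval for the population mean it is too narrow, increasingly so as clearance nears 100%

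*Combined protocol and SAP*

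**What the plan says.** Section 6.3.1 (Change in Lesion Size) takes size as the product of the two longest perpendicular diameters, measured at baseline and at Day 60. Three statements then define the analysis:

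- The only covariate named: "Baseline lesion size will be included as a fixed effect"
- The estimator and its interval: "A mixed model for repeated measures will be used to estimate the mean reduction and its 95% confidence interval"
- The quantity derived for each lesion: "Within-lesion change in lesion size from baseline to the 60-Day follow-up time-point will be calculated"

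Section 3.2 has no comparator: "The study will consist of a single treatment session with the CellFX System", and every subject receives it. Section 3.5 sets the size: "Up to 30 subjects at up to 6 sites will be enrolled". A subject may contribute one or two lesions.

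Section 6.3.1 does not name the model's response variable, the baseline value at which the mean is evaluated, or whether the interval refers to a population of lesions or only to the baselines observed.

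**The concern.** Baseline adjustment sharpens a comparison between arms because it removes variation common to both. Here there is nothing to compare. The quantity of interest is one group's mean change, and variation in baseline size is part of the sampling uncertainty of that mean. A model that conditions on baseline leaves this part out of the standard error.

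The omitted part can be large because reduction is measured in absolute area and is bounded by baseline. Table 4 defines the top category as "CLEAR 0mm/100% reduction", so a cleared lesion's reduction is exactly its baseline size. The more lesions clear, the more closely reduction follows baseline and the smaller the residual variance. A reader could then see a very tight interval from about 30 lesions and take it as precision about the mean reduction to expect in such lesions. The study plans no hypothesis tests, so estimates and intervals are its main output.

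**Working it through.** **Inputs from the documents.** Single arm (3.2); up to 30 subjects (3.5); baseline and Day 60 sizes only (6.3.1, Table 3); "lesion up to 1.5 cm in size with well-defined borders" (4.2.1); cleared means 0 mm (Table 4). The plan gives no SD, expected reduction, clearance rate or CI width, so there is no figure of its own to reproduce.

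**Assumptions.** 30 lesions; longest diameter uniform on 5-15 mm, width 60-100% of length. Uncleared lesions either keep 10-80% of their area or stay unchanged on average with about 10% scatter. Sensitivity runs use diameters of 3-15, 4-15 and 8-15 mm, with partly shrinking lesions keeping 10-70%.

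**Algebra, change as response.** Let D be reduction and B baseline size. The fitted mean at the sample mean of B equals the raw mean of D, so the point estimate does not move. The variances differ:

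- Population mean reduction: Var = SD(D)^2 / n.
- Model with B held fixed: Var = s_res^2 / n, with s_res about SD(D) x sqrt(1 - r^2).
- Omitted term: b^2 x SD(B)^2 / n, where b is the slope of D on B.

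The ratio of CI widths is therefore k = sqrt(1 - r^2), and coverage is roughly 2 x Phi(1.96k) - 1.

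**Numbers put in.**

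- 50% clearance, partial shrinkage: r = 0.82, k = sqrt(1 - 0.672) = 0.57, coverage about 2 x Phi(1.12) - 1 = 74%. Simulation: 74%.
- 70%, partial shrinkage: r = 0.88, k = sqrt(1 - 0.774) = 0.47, coverage about 65%. Simulation: 64%.
- 90%, partial shrinkage: simulated mean half-widths are 4.8 and 18.1 mm2, so k = 4.8 / 18.1 = 0.27 and coverage is about 40%. Simulation: 39%. (The rounded r of 0.95 gives k = 0.31; in simulation the average is lower because some samples contain very few uncleared lesions.)
- 50%, uncleared unchanged: r = 0.41, k = sqrt(1 - 0.168) = 0.91, coverage about 93%. Simulation: 91%.
- 100%: D = B, r = 1, k = 0. Zero width, while the paired half-width is about 15-19 mm2 across the assumed spreads.

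**Simulated coverage of the nominal 95% CI for the population mean, change as response.**

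| Clearance | Uncleared shrink, 5-15 mm | Same, other spreads | Uncleared unchanged, 5-15 mm | Same, other spreads |
|---|---|---|---|---|
| 50% | 74% | 63-79% | 91% | 89-93% |
| 80% | 56% | 44-65% | 81% | 77-88% |
| 90% | 39% | 30-48% | 66% | 59-76% |
| 100% | 0% | 0% | 0% | 0% |

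With uncleared lesions unchanged, coverage at 0-25% clearance is 90-95%. If reduction is unrelated to baseline, the width ratio is 1.00 and coverage 95%. Low clearance alone does not protect the interval: with no lesion cleared but all partly shrunk, coverage is 61-80%. The unadjusted paired interval covers about 93-95% at 50% or more clearance throughout.

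**Other model readings.** One simulated dataset at 90% clearance gives these SEs: paired 10.10; change with baseline covariate 1.56; size at both visits with time plus baseline 7.28; the same with a time-by-baseline term 1.56. For time plus baseline, 7.28 / 10.10 = 0.72, and simulated coverage is about 85-92% at 50-90% clearance and about 84% at 100%, with no collapse to zero width.

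**One or two lesions per subject.** With a subject random intercept, the average SE is 7.73 without the covariate and 1.93 with it, a ratio of 0.25. The random intercept does not cure the problem.

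**The case against.** **The response may be size at both visits.** A single change per lesion is not a repeated measure over time, so the model's name lends this reading support. It reduces the undercoverage but does not remove it, and the spread of SEs from 1.56 to 7.28 in one dataset is itself a reason to specify the model.

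**The interval may be meant as conditional on the observed baselines.** For that target, zero width at full clearance is correct: given these baselines, no uncertainty about the reduction remains. Section 6.3.1 does not state this target, however, and Section 6.5 says the sample was chosen to be representative of BCC lesions, which points to a population mean. The conditional interval is not fully sound either: at 90% clearance it covers its own target only about 81% of the time, because the residuals are skewed.

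**Little depends on it.** This stands. Sections 6.1 and 6.3 make the analysis descriptive, and mean change in size is not among the endpoints in Table 1.

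**Stronger readings to avoid.** A reader might infer that the interval is always far too narrow, or that r is near 1 by construction. The documents do not support this: r was 0.41 in one plausible setting, and the result depends on clearance rate, size spread and response pattern, none of which is given. A reader might also infer that this interval will drive pivotal planning. Section 1.6 says only that the study's data will help design a pivotal study; it does not single out this CI.

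**Conclusion.** The concern holds in conditional form. With change as the response and the population mean as the target, the interval in 6.3.1 omits the sampling variation of baseline size. The loss ranges from negligible (low clearance with no partial response, or reduction unrelated to baseline) to total (every lesion clears). At 90% clearance, coverage is about 39% or 66% under the two main assumptions about uncleared lesions, and 30-76% across all the spreads tried. With size at both visits and a time-plus-baseline model, the undercoverage is mild to moderate. All these figures rest on assumed clearance and size distributions.

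The point estimate is unaffected when evaluated at the mean baseline. So are histological clearance, the lesion reduction category and WHO partial response, since the two size-based measures are computed lesion by lesion. The point is worth correcting because the error bars would be wrong and the remedy is small; it does not threaten the study's conclusions.

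**What to change.** In Section 6.3.1:

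1. State that the response is the within-lesion change from baseline to Day 60 and that the interval is for the population mean reduction.
2. Drop baseline size as a covariate for this interval. Report the unadjusted mean change with a paired interval that allows for two lesions in one subject, by a subject random intercept or a cluster-robust SE.
3. If a baseline-adjusted model is kept, take its CI from a bootstrap that resamples subjects and re-evaluates the adjusted mean at each resample's own mean baseline.
4. Show how reduction varies with baseline size through the lesion-size tertiles already planned in Section 6.7.

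This costs a sentence or two of wording and no extra data. The downside is a wider interval: in the 5-15 mm example at 90% clearance with partial shrinkage, the half-width is 18.1 mm2 instead of 4.8 mm2.
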